5.2 Study Endpoints

Primary Safety Endpoint:

Major Adverse Clinical Events (MAE) at 1 month, defined as death, target vessel revascularization (TVR), target limb amputation.

Primary Performance Endpoint:

Primary Patency at 6 month, defined as no evidence of clinically significant stenosis ($\geq 50\%$) within the stent graft or immediately above or below the treated arterial segment based on duplex ultrasound (systolic velocity ratio of >2.5), with no clinically-driven re-intervention within the stented segment.

Secondary Safety Endpoints:

- Major Adverse Events (MAE) through follow-up.
- Major adverse vascular event (MAVE) through follow-up defined as stent thrombosis, target limb amputation, clinically apparent distal embolization, defined as causing end-organ damage (e.g. lower extremity ulceration, tissue necrosis, or gangrene), procedure related arterial rupture, acute limb ischemia or bleeding event requiring transfusion.
- Major Blood Loss defined as transfusion of >2 units packed red blood cells (PRBC) through discharge.
- The combined rate of death of target vessel revascularization (TVR), index limb amputation, and an increase in Rutherford-Becker Classification by 2 classes (comparing pre- to post-procedural assessments) through follow-up.
- Deep Vein Thrombosis (DVT) on ipsilateral limb defined as a symptomatic blood clot (thrombus) in the targeted deep vein (e.g. posterior tibial) through follow-up.
- VCSS and Villalta Scale through follow-up.
- Venous Assessment (Miller Scale) through follow-up.

- Stent fracture identified via X-ray through follow-up. (Optional per standard practice. Not applicable if radiological Safety Committee approval is required e.g. BFS Germany).

Secondary Performance Endpoints:

- Technical Success defined as successful delivery of the investigational devices to the identified area and removal of delivery system.
- Procedural Success defined as successful delivery of the investigational devices to the identified area and removal of delivery system in the absence of in-hospital MAEs.
- Clinical Success defined as Limb ischemia improvement by Rutherford-Becker (improvement in scale by ≥ 1) through follow-up.
- Limb ischemia by Rutherford-Becker Classification through follow-up.
- Primary Patency through follow-up.

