11.0 ENDPOINTS AND STATISTICAL ANALYSIS PLAN

11.1 Endpoints Analyses and Reporting of Results

The study objective is to assess the safety and performance of the PQ Bypass System to access, deliver guidewires and implant stent grafts for a percutaneous fem-pop bypass.

The study is a feasibility study with no formal hypothesis testing and therefore no required sample size. Study results will be presented using descriptive statistics. Results from this study will be used to design additional clinical studies.

All subjects will be followed on an intent-to-treat basis. The device performance will be assessed based on a per-protocol analysis of the primary safety and effectiveness endpoints. An Intent-to-treat analysis, along with other secondary analyses, will also be completed and reported.

Demographic, baseline clinical and disease characteristics, procedural results and primary, secondary and all additional endpoints will be summarized using descriptive statistics.

All statistical analyses will be performed using SAS for Windows version 9.1 or higher.

Primary Safety Endpoint Reporting:

Safety assessment is achieved by recording and measuring Major Complication rates/Serious Adverse Event rates associated with the PQ Bypass procedure. The number and percentage 6-month MAE will be presented using descriptive Statistics. Using the Score approximation, the one-sided upper 95% confidence bound will be calculated and presented.

Primary Performance Endpoint Reporting:

Descriptive statistics of the primary performance endpoint which includes total number of patent PQB grafts, number and percentage of patent PQB grafts, and the one-sided 95% CI of the percentage using the Score approximation will be presented. The lower bound of the one-sided 95% CI will be compared to the performance goal of 70% (80% historical control rate – 10% Delta.)

Secondary Endpoint Analysis:

The secondary endpoint of primary assisted and secondary patency will be summarized using Kaplan-Meier survival analysis. Life tables will be created and a Kaplan-Meier survival curve will be presented.

The secondary endpoints of Procedural Success, Clinical Success and Technical

Success will be summarized by providing point estimates, number of subjects, and 95% confidence bounds calculated using the Score approximation.

Demographic, procedural and safety data:

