Methods: From March 2004 to May 2005, 100 limbs in 86 patients with femoropopliteal arterial occlusive disease were identified. Patients had symptoms ranging from claudication to rest pain, with or without tissue loss, and were prospectively randomized for treatment into one of two groups. The limbs were treated percutaneously with angioplasty and one or more self-expanding stent grafts (n=50) or surgically with femoral-to-AK popliteal artery bypass using synthetic Dacron or ePTFE grafts (n=50).

The mean and SD total length of artery stented was 25.6 and 15 cm. Follow-up evaluation with ankle-brachial indices and color flow duplex sonography imaging were performed at 3, 6, 9, and 12 months after treatment.

Patients were monitored for a median of 18 months. No statistical difference was found in the primary patency (P=895) or secondary patency (P=.861) between the two treatment groups. Primary patency at 3, 6, 9, and 12 months of follow-up was 84%, 82%, 75.6%, and 73.5% for the stent graft group and 90%, 81.8%, 79.7%, and 74.2% for the femoral-popliteal surgical group. Thirteen patients in the stent graft group had 14 re-interventions, and 12 re-interventions occurred in the surgical group. This resulted in secondary patency rates of 83.9% for the stent graft group and 83.7% for the surgical group at the 12-month follow-up (**Table 11-2**).

Based on review of the limited literature and the recent long lesion stent graft vs prosthetic surgery randomized study 6-month surgical bypass primary patency rate of 82-85% can be extrapolated.

Table 11-2 Randomized Comparison of Viabahn Stent Graft vs. Prosthetic Surgery

Table IV. Primary patency in femoral-popliteal bypass group and stent graft group

Time post-treatment (months)	N at risk at start of interval	N events during interval*	N censored during interval*	% Free from loss of patency	95% CI
Operative (day 0-30)					
Fem-pop bypass	50	2 (2)	0 (0)	0.960	(0.849, 0.990)
Stent graft	50	2 (2)	0 (0)	0.960	(0.849, 0.990)
3 months (day 31-136)					
Fem-pop bypass	48	3 (5)	1 (1)	0.900	(0.776, 0.957)
Stent graft	48	6 (8)	1 (1)	0.840	(0.705, 0.917)
6 months (day 137-227)					
Fem-pop bypass	44	4 (9)	2 (3)	0.818	(0.680, 0.901)
Stent graft	41	1 (9)	1 (2)	0.820	(0.682, 0.902)
9 months (day 228-319)					
Fem-pop bypass	38	1 (10)	8 (11)	0.797	(0.655, 0.885)
Stent graft	39	3 (12)	1 (3)	0.756	(0.611, 0.854)
12 months (day 320-456)					
Fem-pop bypass	29	2 (12)	8 (19)	0.742	(0.587, 0.846)

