19.0 DEFINITIONS

Adverse Device Effect

An adverse event related to the use of an investigational medical device. This definition includes adverse events resulting from insufficient or inadequate instructions for use, deployment, implantation, installation, or operation, or any malfunction of the investigational medical device. This definition also includes any event resulting from use error or from intentional misuse of the investigational medical device.

Adverse Event (AE)

Any untoward medical occurrence, unintended disease or injury, or untoward clinical signs (including abnormal laboratory findings) in subjects, users or other persons, whether or not related to the investigational medical device or index procedure. Adverse events are captured throughout the course of the study.

Allergic Reaction to contrast, polyester, nickel compound of the device and/or anesthesia

An overreaction of the body's immune system to a component of an investigational device (e.g., nitinol metal, polyester, plastics), contrast agents and/or anesthesia medication given to the subject for completion of a study related procedure (e.g., MSCT, angiogram, investigational device), which requires medical intervention to treat the allergic reaction.

Anesthesia Type

Type of anesthesia administered. Categorized as either general, local, or epidural/spinal.

Anticipated Adverse Device Effect (AADE)

An expected effect associated with endovascular treatment of the SFA and may occur during the procedure or during the course of the study. These anticipated effects have been previously identified in the risk analysis report.

Blood Loss

- **Major Blood Loss** - Defined as transfusion of >2 units packed red blood cells (PRBC)).
- **Estimated Procedural Blood Loss** - Defined as the total estimated blood loss (mL) during the index procedure. Includes blood loss resulting from adjunctive procedures performed during the index-procedure.

Clinical Success

Improvement of at least one category using the Rutherford Clinical Severity Scale.

Contrast Volume

Total volume of contrast (mL) administered during the index procedure. Includes contrast administered for adjunctive procedures performed during the index procedure.

Death

Death is divided into two categories and will be reported anytime in a subject's study participation.

- **Device or procedure related death** - Death related to the Study Device or to any procedure (index or subsequent) intended to treat the target vessel.

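### Clinical Success has no condition on re-intervention, surgical bypass or amputation, so a limb that improves only after re-treatment counts as a success of the study device

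*Combined protocol and SAP*

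**What the plan says.** The Protocol Summary and Section 5.2 give the same definition: "Clinical Success defined as Limb ischemia improvement by Rutherford-Becker". The threshold is one category or more, and the period is given only as through follow-up. Section 19.0 has "Improvement of at least one category using the Rutherford Clinical Severity Scale", with no time point. Neither names the reference assessment, and neither mentions re-intervention, surgical bypass or amputation.

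Section 11.1 covers Clinical Success in one sentence with the two other success endpoints, and that sentence ends: "Success will be summarized by providing point estimates, number of subjects, and 95% confidence bounds calculated using the Score approximation". The same section rules out imputation and uses whatever data are available. Section 9.5 has Rutherford class recorded at every visit to 36 months. Section 6.4 keeps all enrolled subjects in follow-up, and no exit or censoring rule applies after a re-intervention.

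Two neighbouring endpoints in Section 5.2 do carry event conditions. Primary patency applies only "with no clinically-driven re-intervention within the stented segment". Procedural Success requires "removal of delivery system in the absence of in-hospital MAEs", and MAE includes TVR and target limb amputation.

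**The concern.** The study objective is the performance of the PQ Bypass System. A subject's study bypass may fail, be re-treated or replaced by surgery, and the limb may then be at least one Rutherford category better than baseline. Nothing in the definition or the analysis removes that subject from the successes. The late rate then measures the study bypass together with whatever followed it, and more re-treatment can hold the rate up while patency falls. Section 11.1 says the results will be used to design further studies, so a late benefit rate read as the device's own could be carried forward.

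The plan also treats the Rutherford scale unevenly. On the harm side, a secondary safety composite in Section 5.2 combines Rutherford worsening with TVR and index limb amputation. On the benefit side, improvement stands alone.

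**Working it through.** **No plan figure to reproduce.** The documents give no expected rate, threshold or power for Clinical Success. The sample sizes in Section 11.2 rest on primary patency and are not affected.

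**Reading the text**

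| Endpoint (Section 5.2) | Condition on later events |
|---|---|
| Primary patency | No clinically-driven re-intervention in the stented segment |
| Procedural Success | No in-hospital MAE (death, TVR, amputation) |
| Clinical Success | None |

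Improvement on this scale is a decrease in category. Entry requires class 3-5, so every subject has room to improve by one category.

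**Size, by assumption.** Let r be the share of limbs re-treated and q the share of those that are better than baseline afterwards. The rate as written minus the rate with re-treatment scored as failure is r × q.

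- Low end: 0.10 × 0.50 = 0.05, or 5 points.
- High end: 0.26 × 1.00 = 0.26, or 26 points.

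The range for q and the 10% are assumptions. The 26% is borrowed for scale from the randomized study cited in Section 11.2: "Thirteen patients in the stent graft group had 14 re-interventions", with 50 limbs in that group and a median follow-up of 18 months, so 13/50 = 26%. This divides patients by limbs (the study had 100 limbs in 86 patients, and the protocol does not give patients per arm), and it concerns a different device and placement.

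**Worked example.** Take N = 100 with 20% re-treated, 80% of those improved, and 90% of the rest improved (all assumed).

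- Not re-treated and improved: 80 × 0.90 = 72.
- Re-treated and improved: 20 × 0.80 = 16.
- As written: (72 + 16)/100 = 88%.
- Re-treatment as failure: 72/100 = 72%.

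Two-sided 95% score interval, with k = 1.96:

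[p + k²/(2n) ± k√(p(1−p)/n + k²/(4n²))] / (1 + k²/n)

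- p = 0.88: 80.2% to 93.0%.
- p = 0.72: 62.5% to 79.9%.

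Both rates come from the same 100 subjects, so the intervals show precision only and do not test the difference.

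**A second yardstick.** In the tables reproduced in Section 11.2, 12-month stent-graft patency was 83.9% secondary and 73.5% primary, so the gap is 83.9 − 73.5 = 10.4 points. Cumulative losses were 8 and 13, and 13 − 8 = 5 of 50 limbs. This concerns patency rather than Rutherford class, so it too indicates scale only.

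**The case against.** The best case for leaving the text alone has four parts.

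1. **Improvement regardless of later treatment is a legitimate patient-level outcome**, and it fits the intent-to-treat follow-up in Section 11.1. This stands, and it is why that rate should be kept as a second line.
2. **The endpoint is secondary and descriptive**, with no hypothesis or decision rule. This stands and limits the stakes.
3. **Primary, primary assisted and secondary patency, TVR and amputation are all reported through follow-up**, so falling durability would be visible. This stands in part. Marginal rates do not show which Clinical Successes were re-treated limbs. Moreover, Section 19.0 words TVR as treatment of a different lesion in the target vessel and keeps index-lesion re-treatment as a separate term that is not a listed endpoint. The primary patency entry there also drops the re-intervention clause.
4. **The size is uncertain.** This stands. The 10.4-point patency gap lies inside the 5-26 range, well below its top. A limb re-treated for a stenosis while the graft was still open may have been improved all along, so r × q is the difference between two rates and not a count of misattributed benefit.

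A reader might infer that every failed study bypass is scored as a success. The documents do not support that: only re-treated limbs that then meet the improvement criterion are affected. A reader might also take the endpoint as assessed at each visit. The wording leaves each visit, last visit and any time open. On an any-time reading, an early improvement would stand despite later failure.

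**Conclusion.** The point holds as an omission. No text states that improvement after re-treatment counts, but the definition as worded counts it and no analysis rule removes it. The late rate would exceed the re-intervention-free rate by about 5-26 points, provided that 10-26% of limbs are re-treated and 50-100% of those are better than baseline. Neither range comes from the documents as a property of this device.

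It would be tempting to quote a firm overstatement of 13-26 points by taking the 26% as the expected re-treatment rate. The documents do not support that, for the reasons given with that figure above, and they say nothing about Rutherford class after re-treatment. Nor does the point reach the primary endpoints or the sample size. It is a low-cost improvement to a secondary endpoint.

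**What to change.** In the Protocol Summary and Sections 5.2, 11.1 and 19.0, define Clinical Success at each named visit, against the baseline Rutherford class, as improvement of at least one category with:

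- no earlier clinically-driven re-intervention on the treated segment, which is the event rule that Section 5.2 uses for primary patency, so that the two endpoints agree;
- no earlier surgical bypass of that segment; and
- no index-limb amputation.

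Report improvement regardless of re-intervention as a second line. Optionally, show ABI and Rutherford class both overall and before the first re-intervention.

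The cost is wording in four places and one extra table row, using data already collected. The downside is a less favourable headline late rate.

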5.3 Study Duration

This study is expected to commence enrollment in the fourth quarter of 2014. Enrollment of all subjects is expected to be completed in the first quarter of 2017. Clinical follow-up will occur at 3 months (± 14 days), 6 months (± 30 days), 12 months (± 45 days), 18 months (± 45 days) 24 months (± 60 days), 30 months (± 60 days), 36 months (± 60 days) following the procedure.

5.4 Number of Subjects and Sites

Up to **60** subjects meeting all inclusion criteria and absent all exclusion criteria, and who are willing to sign informed consent will be enrolled in the **first phase** of the study including:

- Up to 30 subjects in Germany

Up to **100** subjects will be enrolled in the **second phase** of the study (additional 40 subjects) including:

- Up to 30 subjects in Germany

5.5 Inclusion Criteria

Subjects must meet all of the following criteria to be eligible for enrollment in this trial:

- Age 18 or older.

- Willing to comply with the specified follow-up evaluation schedule.
- Women of child bearing potential must have a negative pregnancy test within 7 days prior to the index procedure.
- Severe claudication or rest pain or ischemic ulceration not exceeding ulcer of the digits of the foot (Rutherford Becker scale 3-5) with a resting ABI < 0.9. Resting TBI is utilized only if unable to reliably assess ABI. TBI must be <0.7.
- Subject is not morbidly obese (BMI<40).
- Venous Clinical Severity Score <3.
- Serum creatinine level < 2.0 mg/dL.
- BUN < 20 mg/dL.
- Patent iliac and femoral arteries/veins and access vessels, of sufficient size and morphology (including tortuosity), to allow endovascular access with 8 Fr. introducer sheath.
- Femoro-popliteal lesions ≥10 cm (TASC C and D) in length considered to be:
 - Chronic total occlusion (100% stenosis)
 - Diffuse stenosis (>50% stenosis) with moderate to heavy calcification
 - In-stent restenosis (>50% stenosis)
- Reference vessel diameter (RVD) ≥ 5.0 mm and ≤ 6.7 mm, as measured via pre-screening CTA/MRA using 3D RPR reconstruction.
- Orifice and proximal 1 cm of SFA is patent (approximately 1 cm stump).
- Patent popliteal artery 3 cm proximal to tibial plateau.
- At least 1 patent tibial artery to the foot.
- Patient has the ability to comply with the necessary follow-up examinations and tests in accordance with protocol.
- Patent femoral vein ≥ 10 mm in diameter or duplicate femoral vein.
- Subject has > 2 year life expectancy.

5.6 Exclusion Criteria

Subjects will be excluded from this trial if any of the following criteria are met:

- Age greater than 90.
- History of deep vein thrombosis.
- Has known hypersensitivities, allergies or contraindications to: nitinol, PTFE; aspirin, heparin, antiplatelet, anticoagulant or thrombolytic therapy; or anticoagulation or contrast media.
- Has a known history of intracranial bleeding or aneurysm, myocardial infarction or stroke within the last 3 months.
- Pregnant or nursing.
- Untreated flow-limiting aortoiliac occlusive disease.
- Has renal failure (eGFR < 30mL/min).
- Major distal amputation (above the transmetatarsal) in the study or non-study limb.
- Patient has had a revascularization procedure on the target limb within 7 days of the planned index procedure.
- Known or suspected active infection at the time of the procedure.
- Requires a coronary intervention 30 days or less prior to or 30 days post the treatment of the target lesion.

- Thrombophlebitis, within the previous 30 days.
- Thrombolysis of the target vessel within 72 hours prior to the index procedure, where complete resolution of the thrombus was not achieved.
- Receiving dialysis or immunosuppressant therapy within the previous 30 days.
- Stroke within the previous 90 days.
- Ipsilateral femoral aneurysm or aneurysm in the SFA or popliteal artery.
- Planned amputation of the target limb.
- Previous bypass surgery on the target limb.
- Participating in another clinical study for which follow-up is currently on going which may impact the current study.
- Congestive heart failure, COPD (Stage IV, FEV1 <30% normal, or <50% normal with chronic respiratory failure present), metastatic malignancy, dementia, or other major co-morbidities that would prevent the post-interventional movement.
- A condition that in the view of the investigator precludes participation in this study.

6.0 SUBJECT ENROLLMENT INFORMATION

6.1 Written Informed Consent

Subjects who meet general entry criteria will be asked to sign the study specific Ethics Committee (EC) approved Informed Consent form before any study-specific tests or procedures are performed. Study personnel should explain that even if a subject agrees to participate in the study and signs an Informed Consent Form, the subject may not be eligible to participate if he/she fails screening criteria.

A Screening/Enrollment Log will be maintained to document select information about candidates who fail to meet the entry criteria.

6.2 Enrollment

Subjects will be considered enrolled into the study once informed consent has been signed and all eligibility criteria confirmed. Investigators will access the target artery and the corresponding ipsilateral vein using standard percutaneous techniques and devices. Patient eligibility will be confirmed prior to insertion of the study device, based on procedural angiogram and sheath placement.

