6.4 Withdrawal of Subjects

Each subject may voluntarily withdraw his/her participation from the study at any time. Investigators may discontinue a subject's participation in the study as deemed appropriate per safety measures and/or if the subject's medical condition contraindicates further study participation. All enrolled subjects will undergo the complete study follow-up for safety evaluation.

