7.0 RISK-BENEFIT ASSESSMENT

7.1 Risks

There are standard risks associated with any interventional procedure or stent graft placement as well as risks specific to the PQ Bypass devices and procedure. Risks associated with any interventional procedure include access site hemorrhage or hematoma, access site pain, acute vessel closure, infection, renal insufficiency/failure due to excessive contrast load, and death. The risks stated below concern each system manufactured by PQ Bypass and their use in the PQ Bypass procedure.

Possible risks related to the PQ Bypass Guidewire Delivery System include, but are not limited to, the following: vessel dissection, perforation or wall trauma, embolism, infection, bruising or hemorrhage at the procedural access site, deep vein thrombosis, bleeding or infection.

Possible risks related to the PQ Bypass Stent Graft System include, but are not limited to, the following: thrombosis, stenosis or occlusion, aneurysm or pseudoaneurysm formation, vessel dissection, perforation or wall trauma, embolism, venous flow disruption (including deep vein thrombosis, edema or phlebitis), arteriovenous fistula formation, bleeding infection or side branch occlusion.

Additionally, subjects will be exposed to risks associated with conscious sedation, use of radiographic contrast and procedural medications. Subjects will be asked to take anti-platelet medication for this study, such as aspirin for life and Plavix

(clopidogrel) or Ticlid (ticlopidine) for length of follow-up. These medications have been approved to reduce the risk of cardiovascular events. An Investigator will discuss with each subject the standard risks associated with these medications.

Risk will be mitigated by working with Investigators who are experienced and skilled in endovascular techniques including use of re-entry tools and stent graft placement. Additionally, each Investigator will be thoroughly trained on proper device operation prior to device use. Risks will also be minimized in this study by adhering to the inclusion/exclusion criteria. For example, subjects with known allergies or contraindications to study medications (contrast, anti-platelet, heparin) will be excluded. Risks associated with device malfunctions or failures will be minimized through bench and in-vivo animal verification and validation testing prior to use in this study.

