9.3 Procedural Evaluation

Final eligibility will be determined based on imaging study and sheath placement. Information on the lesion being treated and the specific vasculature used in its treatment will be collected. The procedural evaluation will consist of the following:

- Lesion length
- Lesion calcification (TASC II Classification)
- Lesion type
- Procedure time

- Access sites used
- Number of attempts to create each anastomosis
- Complications or adverse events

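### Consented subjects whose case stops at vascular access, before eligibility is confirmed, are never enrolled, and the plan gives them no assured safety follow-up and no place in any safety denominator

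*Combined protocol and SAP*

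**What the plan says.** Section 6.2 defines enrollment: "Subjects will be considered enrolled into the study once informed consent has been signed and all eligibility criteria confirmed". It then describes vascular access, "Investigators will access the target artery and the corresponding ipsilateral vein using standard percutaneous techniques and devices", and places the final check after that access and before any study device: "Patient eligibility will be confirmed prior to insertion of the study device, based on procedural angiogram and sheath placement". Section 9.3 agrees: "Final eligibility will be determined based on imaging study and sheath placement". Section 8.1 gives the same order, and the Schedule of Assessments puts the final eligibility angiogram and venogram in the procedure column. One inclusion criterion in 5.5 requires vessels of suitable size and shape "to allow endovascular access with 8 Fr. introducer sheath".

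On follow-up, 6.4 says "All enrolled subjects will undergo the complete study follow-up for safety evaluation". For screen failures, the log in 17.2 holds dates, enrollment status and the reason for exclusion. Section 11.1 names intent-to-treat and per-protocol analyses but defines neither set.

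**The concern.** The study procedure begins with puncture of an artery and of the vein on the same side, in subjects who have already consented. The vein is entered because the bypass route runs through it (8.1). Section 7.1 lists "access site hemorrhage or hematoma, access site pain, acute vessel closure" among the risks of any interventional procedure. Several endpoint components can follow from such an injury: arterial rupture, acute limb ischemia or transfused bleeding in MAVE, Major Blood Loss, ipsilateral DVT, and death within MAE.

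Because the enrollment point lies after this exposure, an access complication that prevents confirmation also removes the subject from the denominators. Milder access injuries, where the case goes on, stay in. If such subjects exist, the selection would tend to make procedural safety look better than it was, and a single-arm study has no control group subject to the same selection.

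**Working it through.** **Sequence of events, from 6.2, 8.1 and 9.3**

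1. Consent is signed.
2. Initial eligibility: CTA or MRA, and venous ultrasound (9.1).
3. Arterial and venous access with standard devices, then procedural imaging.
4. Final eligibility is confirmed. The subject is now enrolled.
5. The Venous Locator, Percutaneous Anastomotic Device and Balloon Dilator are used, then the stent grafts.

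**Who is counted**

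- Stopped at step 3 because eligibility cannot be confirmed: not enrolled. Follow-up under 6.4 is not assured, and no analysis set in 11.1 is said to include the subject.
- Access injury at step 3, eligibility still confirmed: enrolled, so the injury counts. This holds even if the case then stops before a device goes in.
- Failure or injury at step 5: enrolled and counted. Section 8.1 also records the number of attempts at each anastomosis.

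Only the first group is affected.

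**The plan's own figures**

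The documents give no count of access-only subjects, so there is no stated figure to reproduce on this point. The patency sample sizes in 11.2 do not depend on the enrollment point. They reproduce from n = [1.645·√(p0(1−p0)) + 0.842·√(p1(1−p1))]² / (p1−p0)² with p1 = 0.85: p0 = 0.70 gives 49.4, so 50; p0 = 0.75 gives 102.6, so 103.

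**Illustration (all counts are assumptions)**

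The one-sided 95% Score upper bound, with z = 1.645, is

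U = [p + z²/(2n) + z·√(p(1−p)/n + z²/(4n²))] / (1 + z²/n).

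Section 11.1 specifies this bound for MAE; it is borrowed here for MAVE. For 4/100: U = [0.04 + 0.0135 + 1.645·√(0.000384 + 0.0000676)] / 1.0271 = 0.086.

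| Assumed case | Events / subjects | Rate | Upper bound |
|---|---|---|---|
| Enrolled only | 4/100 | 4.0% | 8.6% |
| Plus 5 access-only, 0 events | 4/105 | 3.8% | 8.2% |
| Plus 5 access-only, 1 event | 5/105 | 4.8% | 9.5% |
| Plus 10 access-only, 3 events | 7/110 | 6.4% | 11.3% |

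The last two rows assume event rates of 1/5 = 20% and 3/10 = 30% in access-only subjects. The combined rate exceeds the enrolled rate only if access-only subjects have events more often than enrolled subjects. With no access-only subjects, nothing changes.

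**The case against.** The strongest reply is that enrolling at final confirmation, just before the device goes in, is a coherent choice for a device study. The access at issue uses standard techniques and devices, and 7.1 lists its risks under interventional procedures in general, before those specific to the PQ Bypass devices. This stands, and it is why the enrolled set should remain the main one.

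A reader might go further and infer that the study's own access step goes uncounted, since 11.1 states the aim as "to assess the safety and performance of the PQ Bypass System to access, deliver guidewires and implant stent grafts". The documents do not support that. The investigational crossing comes after eligibility confirmation, and the protocol also uses the word access for the work of the device's needle (3.1) and for guidewire placement at each anastomosis (8.1).

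Nor is every safety and success endpoint affected. Injuries in subjects who proceed still count. Technical Success is defined on delivery of the investigational devices, so a failed standard sheath is arguably outside it, and charging such failures against that rate would not be justified.

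It would also be wrong to say that these events leave no trace. Adverse events are assessed at the procedure; 12.2 requires serious events to be reported whether or not related; 12.4 says that all incidents are captured; and 14.1 requires source documents, including adverse events, for subjects who undergo screening. These provisions can reach access-only subjects. They do not assure follow-up to a fixed time or place the events in any analysis.

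Two further points limit the concern. Pre-procedural imaging should find some unsuitable vessels before any puncture. The enrollment flowchart is not legible in the available text, so it may show how these subjects are handled.

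**Conclusion.** The point holds in a narrow form, as a cheap improvement and not as an error that undermines a result. By the stated rule, consented subjects stopped at access before eligibility is confirmed fall outside the MAE, MAVE, Major Blood Loss and DVT denominators, and their safety follow-up is not assured.

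Any downward bias in procedural safety rates is confined to this group. Its size cannot be found from the documents. Under the assumptions shown, it ranges from nothing to about 2.4 percentage points (6.4% − 4.0%). No safety threshold is set in the plan, so none would be crossed, and the patency comparison and sample size do not change. The conclusion rests on reading 6.2 as written and on there being no rule elsewhere in the legible text for subjects stopped at access.

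**What to change.** Keep the enrolled set for patency, for Technical and Procedural Success and for the main safety rates. Then:

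- In 6.2 and 11.1, define a supplementary safety set: all consented subjects in whom arterial or venous access for the study procedure was attempted.
- Follow access-only subjects for adverse events to a 1-month contact.
- Report their number, reason for stopping, and MAE, MAVE, Major Blood Loss and DVT events, both separately and combined with the enrolled set.
- Report sheaths placed / attempted as its own line, apart from Technical Success.

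The cost is protocol and analysis wording, plus one extra contact and an adverse event form for what should be a few subjects. The supplementary safety rates may be slightly less favourable. For subjects already past this stage, the screening log (17.2) and source documents (14.1) may allow partial recovery.
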